#### Secondary Analysis

We plan to conduct a number of pre-specified analyses of secondary study endpoints. Analyses of secondary “time-to-event” type endpoints (time to retroprosthetic membrane treatment and time to

occurrence of vitritis) will use the Kaplan-Meier approach with log-rank test and Cox proportional hazards regression, similar to the primary analysis for time to device loss.

Comparison of cornea thickness metrics at week 1, 4, 16, 24, and 52 for treatment versus control group will be performed using the Mann-Whitney Wilcoxon test at each time point.

Furthermore, a mixed model regression analysis using generalized estimating equations (GEE) with compound symmetry covariance structure for repeated measures will be used to examine the effect of time, treatment and the interaction between them on cornea thickness to evaluate the change over time between and within the treatment groups. Comparison of twelve-month retention rate and incidence of delayed epithelial healing at Day 30 (week 4 visit) between groups will be performed using Chi-square test, or Fisher's exact test as appropriate.

In addition, the occurrence of any adverse events will be described and compared between treatment arms of the study.

We will run multivariable analysis with relevant information from the subject's ocular history to determine if certain characteristics inform or predict the loss of the study KPro or the survival time between insertion and removal. Among these, we will include age at study surgery, sex, race and whether patients- had previous KPros in the study eye and, if so, how many. For the subset of patients who did have previous Kpros in the study eye, we will look at the survival time of the one immediately before the study eye and compare it to the survival time of the study one. We will compare mean duration for these and analyze if there is a statistically significant difference among those who received a collagen cross-linked carrier cornea versus those who did not.

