6.8 Rescue Medication or Therapy

Subjects who do not retain the cross-linked KPro will be withdrawn from the study and the cornea will be replaced with a cadaver cornea or standard KPro at the physician's discretion.

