10.3 Termination, of Subjects due to Adverse Events

Termination from the study will happen if any of the following occurs:

- Subject's wish to withdraw for any reason.

- Investigator or Research Monitor determination that it is not in the best interest of the subject to continue participation
- KPro removal

In the event an adverse event in the study eye is severe enough to require the donor study tissue to be removed and replaced with fresh cadaveric human cornea donor tissue with or without a keratoprosthesis, the patient will be terminated from further participation in the study. However, prior to termination the patient will be followed for 30 days after replacement surgery to collect any additional event data.

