## N = 68 subjects

**Preliminary Results:** Sixty-eight Kpros were implanted in 68 eyes (56 with previous sterile corneal ulceration) in 68 patients (15 with autoimmune disease) between 2017 - 2020 across 13 sites. The average age at the time of surgery was 62 [24-89] years, 42 (62%) subjects were male and 44 (65%) were white. The mean follow-up time was 91 weeks (SD= 47.6). A total of 20 KPros were removed with an average survival time of 70 [6-160] weeks.

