### Secondary endpoints or outcome measure(s)

- Twelve-month retention rate
- Incidence of delayed epithelial healing at day 30 (week 4 visit)
- Time from surgery to retroprosthetic membrane treatment (laser or surgical interventions)
- Time from surgery to occurrence of vitritis (sterile or infectious)
- Time from surgery to occurrence of ocular surgery to address melt, including partial graft.
- Cornea thickness metrics measured by AS-OCT; at week(s) 1, 4, 16, 24, 36, and 52\*\*\*

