### Previous KPro

- Previous KPro in the study eye: yes/no
  - If yes, how many, how long were they in the eye for and why were they removed.
  - We don't have exact dates for all previous ones since some were done at other hospitals.

Reorganize the primary and secondary outcome measures into:

- Efficacy endpoints:
  - Removal or not of the study KPro
  - Rate of retention at 52 weeks
  - Time from KPro study surgery to ocular surgery done to address a melt, including partial graft

- Safety endpoints:
  - Incidence of delayed epithelial healing at day 30 (week 4 visit)
  - Time from surgery to retroprosthetic membrane treatment (laser or surgical interventions)
  - Time from surgery to occurrence of vitritis (sterile or infectious)

We will conduct an initial analysis to examine if distributions of baseline characteristics are balanced between the two treatment groups in our randomized study. Standard descriptive statistics will be reported, median (min-max) for numerical variables and frequency count (%) for categorical variables. Comparisons of numerical characteristics between treatment groups will be conducted using the Mann-Whitney U- test. Comparisons of categorical characteristics will be conducted using Chi-square, or Fisher's exact test as appropriate.

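### The Kaplan-Meier plan for membrane treatment and vitritis does not say how KPro removal is handled; if removal is censored, 1-KM read as incidence is too high, by about 3 to 5 points at two years at the pooled removal rate.

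*SAP*

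**What the plan says.** The SAP lists time to membrane treatment and time to vitritis as secondary endpoints and, under Previous KPro, regroups both as safety endpoints. The vitritis endpoint reads "Time from surgery to occurrence of vitritis (sterile or infectious"), with no restriction to the period when the study device is in the eye. The SAP's Secondary Analysis "will use the Kaplan-Meier approach with log-rank test and Cox proportional hazards regression, similar to the primary analysis for time to device loss" for these two endpoints, and Protocol 11.5 has the same plan. Neither document gives a censoring rule for them, names a competing event or plans a cumulative incidence estimate.

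On what happens at device loss, Protocol 6.8 says "Subjects who do not retain the cross-linked KPro will be withdrawn from the study" and that "the cornea will be replaced with a cadaver cornea or standard KPro at the physician's discretion". Although 6.8 speaks only of the cross-linked device, Protocol 10.3 lists KPro removal as a reason for termination in any subject. Section 10.3 adds that, where an adverse event requires the tissue to be replaced, "prior to termination the patient will be followed for 30 days after replacement surgery to collect any additional event data".

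The SAP's opening summary reports "A total of 20 KPros were removed with an average survival time of 70 [6-160] weeks", from 68 eyes with a mean follow-up of 91 weeks, arms pooled. Under Primary Analysis the SAP also plans a composite of KPro removal or melt surgery, whichever comes first. It plans nothing similar for membrane treatment or vitritis.

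**The concern.** An eye that loses its study KPro leaves the study, so almost nothing that happens to it later is observed. If such eyes are censored, they drop out of the risk set, and Kaplan-Meier assumes that their later hazard equals that of eyes still being followed. The curve then describes a setting in which no device is ever removed. That is not the proportion of implanted patients who go on to have membrane treatment or vitritis, which is how a surgeon or patient will read a safety curve.

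Removal is also the primary endpoint, and the sample size assumes that it differs between arms (Protocol 11.3). If it does, the gap between 1-KM and actual incidence differs by arm. Suppose cross-linking improves retention and leaves the event hazard unchanged. Treated eyes then stay at risk longer and a larger share of them have the event, while the two Kaplan-Meier curves coincide.

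The assumption behind the censoring is itself doubtful. Protocol 1.1 describes melting as leading to both exposure to pathogens and extrusion, so device loss and infectious vitritis can share a cause.

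**Working it through.** The documents give no incidence for either endpoint, so there is no stated figure to reproduce. The check compares 1-KM with cumulative incidence under constant cause-specific hazards.

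**Inputs**
- Removals: 20 (SAP, opening summary).
- Device time at risk: 68 eyes × 91 weeks / 52 = 119 person-years. This treats mean follow-up as time with the device in place. If it included 30 days after each of the 20 removals, the time would fall by 20 × 30/365 = 1.6 years and the rate would be 0.170 rather than 0.168.
- Pooled removal hazard: l = 20/119 = 0.168 per year, which implies 12-month retention of exp(-0.168) = 84.5%.
- Event hazard a: not in the documents. Assumed to be 0.1 to 0.2 per year.

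**Formulas**
- 1-KM with removal censored = 1 - exp(-aT).
- Cumulative incidence with removal as a competing event = a/(a+l) × [1 - exp(-(a+l)T)].

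**Worked case, a = 0.2, T = 2**
- 1-KM = 1 - exp(-0.4) = 33.0%.
- Cumulative incidence = 0.2/0.368 × [1 - exp(-0.736)] = 0.543 × 0.521 = 28.3%.

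**Results at the pooled removal rate**

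| Assumed event hazard | Time | 1-KM | Cumulative incidence | Difference |
|---|---|---|---|---|
| 0.1/yr | 1 year | 9.5% | 8.8% | 0.7 points |
| 0.2/yr | 1 year | 18.1% | 16.7% | 1.4 points |
| 0.1/yr | 2 years | 18.1% | 15.5% | 2.6 points |
| 0.2/yr | 2 years | 33.0% | 28.3% | 4.7 points |

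**Dependence on the arm split.** Person-time is assumed equal, 59.5 years per arm, with a = 0.2 and T = 2. The splits are illustrations, since the documents give none.
- 10:10 removals: both arms have hazard 0.168, and the overstatement is 4.7 points in each.
- 14:6 removals: hazards are 14/59.5 = 0.235 and 6/59.5 = 0.101, and the overstatements are 6.3 and 2.9 points.

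**Check on the planning rates.** Protocol 11.3 uses 12-month retention of 55% and 85% as its middle case.
- The hazards are -ln(0.55) = 0.598 and -ln(0.85) = 0.163 per year.
- With a = 0.2 at two years, cumulative incidence is 20.0% in control and 28.4% in treatment, against 33.0% by 1-KM in both.
- The control hazard does not fit the SAP's data. Even if all 20 removals were in control, its hazard would be 20/59.5 = 0.336 and its two-year cumulative incidence 24.5%. A hazard of 0.598 would need all 20 removals to fall within 20/0.598 = 33 control person-years.

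**The case against.** The strongest reply is that the SAP never says it will censor at removal or quote 1-KM as an incidence, and that the between-arm tests it does name are sound. Both parts are right. Censoring is inferred from the withdrawal rules together with a standard Kaplan-Meier analysis, and log-rank and Cox with censoring at removal validly compare cause-specific hazards. The SAP also plans to describe and compare adverse events by arm, so raw counts should be available beside any curve. What survives is that the plan is silent on an event affecting 20 of 68 eyes, and that a Kaplan-Meier curve for a safety event invites the incidence reading.

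A reader might infer three stronger points that the documents do not support.
- **That the overstatement is known to be larger in control, as much as 33% shown against 20% true.** That rests on the planning retention of 55%, which the pooled removal data contradict. An equal split of removals would give equal overstatement.
- **That removal strictly precludes the event.** The vitritis endpoint is not tied to the study device, the replacement may be a standard KPro, and section 10.3 allows 30 days of further data. Vitritis, or a membrane behind a replacement device, can still occur but would mostly go unobserved.
- **That melt surgery is left wholly exposed to the same problem.** The composite under Primary Analysis already counts removal as an event. Only the standalone time to melt surgery is open, and the Secondary Analysis does not list it among the endpoints given a method.

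**Conclusion.** The concern holds as a gap in the handling of two safety endpoints. If removal is censored, 1-KM read as incidence exceeds the share of patients who have the event, by about 1 point at one year and 3 to 5 points at two years. These sizes assume constant hazards, an event hazard of 0.1 to 0.2 per year, and 68 × 91 weeks of device time at risk. The overstatement is unequal if removals differ by arm, which the design assumes but the pooled data neither confirm nor refute, so the documents do not allow its size by arm to be stated. The log-rank and Cox comparisons stand as cause-specific results. The primary analysis and the sample size are not touched.

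**What to change.** Amend the SAP's Secondary Analysis as follows.
- Define time to membrane treatment and time to vitritis as events with the study KPro in place, and state how events in the 30-day window after replacement surgery count.
- Report Aalen-Johansen cumulative incidence by arm, with KPro removal and death as competing events.
- Keep log-rank and Cox, labelled as comparisons of cause-specific hazards.
- Give the standalone time to melt surgery the same treatment, alongside the planned composite.
- Report removals and device time at risk by arm, so that readers can judge how far the two kinds of curve diverge.

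The cost is a few SAP sentences and a standard software routine, with no new data collection. The downside is one extra estimate to explain next to the cause-specific hazard ratio, and the two can point in different directions when retention differs by arm.

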8.5 Standard of Care Procedures

The following procedures will be performed as standard of care and included in study analysis:

- At screening:
 - Informed consent (must be obtained before screening starts and before surgery)
Record current ocular and systemic medications
 - Record significant medical/surgical history in the past 5 years
 - Record demographic data, including date of birth, sex, and race/ethnicity
 - Review of Systems
 - Constitutional, Ear/Nose/Throat, Respiratory, Cardiovascular, Gastrointestinal, Genital/Urinary, Integumentary, Musc/Skeletal, Endocrine, Heme/Lymph, Allergic/Immun, Neurologic, Psychiatric, All Others
 - Best corrected VA assessment at 4 meters (with refraction)
 - Intraocular pressure (measured by digital palpation)
 - Slit lamp examination

- Slit lamp photography

- Funduscopy (Ultrasound B-Scan will be performed, if necessary).

Historical results for best corrected VA, intraocular pressure, slit lamp examine, slit lamp photography and funduscopy can be used if completed within 60 days prior to screening visit

- At day 0:

- Keratoprosthesis implantation

- At day 1:

Day 1 visits will be performed by MEE clinical staff (physicians) that are not study investigators. Post-operative appointments with physicians are standard of care treatments for patients that have surgery. However study investigators that perform the surgery often do not hold clinical appointments every day of the week and therefore are unable to see the patients for the Day 1 visit. In order to ensure subject safety study patients are scheduled with available MEE physicians. The following procedures are performed as standard of care.

Study staff will collect the data from these exams from the subject's medical record.

- Best corrected VA assessment at 4 meters (with refraction)
- Intraocular pressure (measured by digital palpation)
- Slit lamp examination
- Funduscopy/ Ultrasound B-Scan (if necessary)

- At weeks 1, 4, 16, 24, 36, and 52:

- Best corrected VA assessment at 4 meters (with refraction)
 - Intraocular pressure (measured by digital palpation)
 - Slit lamp examination
 - Funduscopy/ Ultrasound B-Scan (if necessary)
 - Slit Lamp Photography
 - Cornea thickness as measured by AS-OCT

- At all times following day 0:
 - Topical steroids
 - Topical antibiotics
 - Bandage contact lens

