11.2 Secondary endpoints or outcome measure(s)

- Twelve-month retention rate
- Incidence of delayed epithelial healing at day 30 (week 4 visit)
- Cornea thickness metrics measured by AS-OCT; at week(s) 1, 4, 16, 24, and 52.
- Time from surgery to retroprosthetic membrane treatment (laser or surgical interventions)
- Time from surgery to occurrence of vitritis (sterile or infectious)
- Time from surgery to occurrence of ocular surgery to address melt, including partial graft.

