We plan to conduct a number of pre-specified analyses of secondary study endpoints. Analyses of secondary “time-to-event” type endpoints (time to retroprosthetic membrane treatment and time to occurrence of vitritis) will use the Kaplan-Meier approach with log-rank test and Cox proportional hazards regression, similar to the primary analysis for time to device loss. Comparison of cornea thickness metrics at week 1, 4, 16, 24, and 52 for treatment versus control group will be performed using the Mann-Whitney Wilcoxon test at each time point. Furthermore, mixed model will be used to examine the effect of time, treatment and interaction between them on cornea thickness. Comparison of twelve-month retention rate and incidence of delayed epithelial healing at Day 30 (week 4 visit) between groups will be performed using Chi-square

test, or Fisher's exact test as appropriate. In addition, the occurrence of any adverse events will be described and compared between treatment arms of the study.

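### The corneal-thickness analyses omit the week-36 scans, name two different models in one sentence, and from week 16 on compare retained eyes only without saying so

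*SAP*

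**What the plan says.** **Visits.** Protocol 8.5 schedules corneal thickness by AS-OCT "At weeks 1, 4, 16, 24, 36, and 52". The SAP endpoint list agrees: "Cornea thickness metrics measured by AS-OCT; at week(s) 1, 4, 16, 24, 36, and 52". Protocol 9.3 lists the same six visits. Protocol 11.2 has five: "Cornea thickness metrics measured by AS-OCT; at week(s) 1, 4, 16, 24, and 52". The test plan in the SAP's Secondary Analysis also has five, "Comparison of cornea thickness metrics at week 1, 4, 16, 24, and 52 for treatment versus control group", as does Protocol 11.5. No reason is given for dropping week 36.

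**Model.** The SAP says that "a mixed model regression analysis using generalized estimating equations (GEE) with compound symmetry covariance structure for repeated measures will be used". Protocol 11.5 says: "Furthermore, mixed model will be used to examine the effect of time, treatment and interaction between them on cornea thickness". Neither sentence names the visits to be modelled.

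**After removal.** Protocol 6.8: "Subjects who do not retain the cross-linked KPro will be withdrawn from the study". Protocol 10.3 lists KPro removal, without limiting it to one arm, as a ground for termination; before that, "the patient will be followed for 30 days after replacement surgery to collect any additional event data". Protocol 8.6 treats thinning as a sign of melting. The SAP's intent-to-treat statement covers the primary efficacy analysis, Protocol 11.4 (Analysis Population) is marked not applicable, and the SAP gives no population or missing-data rule for thickness.

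**The concern.** An endpoint defined at six visits is tested at five, and no test falls in the 28 weeks between weeks 24 and 52. Two analysts following the SAP's model sentence could fit different models. GEE in its usual unweighted form needs data missing completely at random, whereas a likelihood-based mixed model needs only missing at random. The distinction is relevant here because thickness stops being recorded when a carrier is removed, and a thin carrier may be the one that is removed.

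For the same reason, the later visit tests compare the eyes still holding their carrier. If cross-linking works as hoped, the control arm loses more of its thinnest eyes, and the remaining control eyes look better than the arm as a whole. At stake are the size and power of a secondary comparison, and whether a reader takes it as a comparison of all randomised eyes.

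**Working it through.** The plan states no expected thickness, sample size or power for this endpoint, so there is no figure of its own to reproduce.

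**1. Visit lists side by side.** With week 36: Protocol 8.5, Protocol 9.3, SAP endpoint list. Without: Protocol 11.2, Protocol 11.5, SAP Secondary Analysis. The omission affects the per-visit tests; the model may already use week 36, since its sentence lists no visits.

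**2. Which visits removal can affect.** The SAP's preliminary results give 20 removals among 68 eyes, at 6 to 160 weeks. The week-4 visit has a window of ±3 days, so it precedes the first removal. Only week 16 onward can be affected.

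**3. Removals by week 52.** Reading the stated average of 70 weeks as a mean, the 20 times sum to 20 × 70 = 1400.
- Sixteen by week 52 is possible: at most 6 + 15×52 + 4×160 = 1426 ≥ 1400.
- Seventeen is not: 6 + 16×52 + 3×160 = 1318 < 1400.
- One is possible: with one at 6 and one at 160, the other 18 average (1400 − 166)/18 = 68.6 weeks.

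So the range is 1 to 16. For illustration, a constant hazard over the mean follow-up of 91 weeks is 20/(68×91) = 0.0032 per week. This gives 68×(1 − e^(−0.00323×52)) = 10.5 removals by week 52, of which 5.4 fall after week 24 and 3.1 after week 36.

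**4. Size under assumed thickness values.** All inputs here are assumptions: 34 eyes per arm; starting thickness 560 µm (SD 45); slopes −1.0 (control) and −0.3 (treated) µm/week; measurement SD 15; between-eye slope SD 0.3 to 1.3. Every removal is driven by thinness, with probability 0.5 per interval below a threshold set to give the stated number of losses. The driver is either the last recorded reading or an unrecorded thickness. There were 1500 simulated trials per setting. The slopes imply 0.7×52 = 36.4 µm at week 52; the simulated full-data means were 35.0 to 35.6, and bias is measured against these. GEE uses an exchangeable correlation; REML is the mixed model with unstructured covariance.

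Ten losses, week 52:

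| Driver | Slope SD | Bias (µm): retained / GEE / REML | Mann-Whitney power: full / retained / removed ranked worst |
|---|---|---|---|
| recorded | 0.3 | −4.8 / −0.4 / +0.1 | 0.80 / 0.74 / 0.73 |
| recorded | 0.5 | −5.1 / −0.8 / +0.1 | 0.72 / 0.65 / 0.66 |
| recorded | 1.0 | −6.0 / −2.2 / +0.2 | 0.50 / 0.40 / 0.46 |
| recorded | 1.3 | −6.6 / −3.2 / +0.2 | 0.39 / 0.30 / 0.36 |
| unrecorded | 0.3 | −9.0 / −1.2 / −0.9 | 0.80 / 0.60 / 0.78 |
| unrecorded | 0.5 | −8.9 / −2.1 / −1.3 | 0.72 / 0.54 / 0.71 |
| unrecorded | 1.0 | −9.2 / −4.3 / −1.5 | 0.50 / 0.35 / 0.49 |
| unrecorded | 1.3 | −9.5 / −5.3 / −1.5 | 0.39 / 0.26 / 0.39 |

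At five losses, retained-eye bias is −3.5 to −6.4 µm, and power is 0.04 to 0.11 below full data (0 to 0.02 below with removed eyes ranked worst). If only half of ten losses are thinness-driven, retained-eye bias is −3.7 to −6.7 µm. If loss is unrelated to thickness, all three estimates are within 0.2 µm of the truth. Leaving out week 36 moves the GEE by at most 0.3 µm and REML by at most 0.7 µm.

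**The case against.** A removed carrier has no thickness, so retained eyes are the only eyes a per-visit test can use, and the SAP never claims an all-randomised comparison for this endpoint. Lost eyes already count in the primary endpoint and in the SAP's added composite of removal or melt surgery. All of that stands. The complaint is that the comparison is unlabelled, not that it could be made differently. A worst-rank analysis does partly repeat the primary endpoint.

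The model choice also matters little in numbers. GEE bias is at most 0.35 standard errors in the main grid, its 95% interval coverage is 0.92 to 0.94, and root mean square error is 12–20 µm against 12–21 for REML. The case for one model is clarity and agreement with Protocol 11.5.

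A reader might infer more than the documents support:
- *That dropping week 36 biases the results.* It discards data and contradicts the endpoint definition; it does not distort the other visits.
- *That every visit test is affected.* Weeks 1 and 4 are not.
- *That the retained-eye tests would often show false harm.* With the planning retention of 0.55 against 0.85, 34 eyes per arm, a correlation of 0.8 between thickness and retention and no true difference, false significance against cross-linking reaches 28.3%. But this needs 34×(0.45 + 0.15) = 20.4 losses by week 52, more than the 16 that the preliminary results allow. In the grid above with no treatment effect, type I error of the retained-eye test is 0.045 to 0.058.

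**Conclusion.** The point holds as a matter of consistency and labelling for a secondary endpoint. The week-36 contradiction and the two-model sentence are in the current text and need no assumption. That the tests from week 16 on use retained eyes only follows from the withdrawal rules.

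The direction and size of any bias are conditional. If thin control carriers are removed more often, protection is understated: 14 to 27% of the assumed difference at ten thinness-driven losses, with week-52 power 0.06 to 0.20 lower. If removal is unrelated to thickness, there is little or no bias. The documents give no thickness values, removals by arm or reasons for removal, so these figures are illustrations, not estimates for this trial. The primary log-rank analysis is unaffected. The change should be made, but the trial's main conclusion does not depend on it.

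**What to change.** 1. Add week 36 to all thickness analyses in the SAP's Secondary Analysis, and align Protocol 11.2 and 11.5.
2. Name one model: a likelihood-based mixed model, as in Protocol 11.5, with arm, categorical visit (1, 4, 16, 24, 36, 52) and arm-by-visit. State the covariance and a simpler fallback in advance. An unstructured matrix for six visits has 6×7/2 = 21 parameters, which 68 eyes may not support; a random intercept and slope gave results within 0.2 µm of it in the simulations.
3. Report the Mann-Whitney tests as comparisons among retained eyes, with numbers measured per arm and visit.
4. Add a week-52 rank sensitivity analysis with removed eyes at the worst rank, for any removal, or for removal due to melt where existing records show it.

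The cost is SAP wording, two protocol passages and a little more analysis. No new data are needed; the melt-only version needs a review of existing records. The downsides are about the same total error as the GEE, partial overlap of the rank analysis with the primary endpoint, and some remaining bias if carriers thin and are removed between visits.
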